### 6.3.6 Adverse Events

Adverse events (AEs) are to be monitored throughout the course of the clinical trial. All AEs are to be reported on the Adverse Event Form with complete information as required. If AEs occur, the main concern will be the safety of the subjects. At the time of the ICF signature, each subject must be provided with the name and phone number of clinical trial center personnel for reporting AEs and medical emergencies.

## 6.3.6.1 Definitions

### 6.3.6.1.1 Adverse Events

According to ICH E2A, an AE is any untoward medical occurrence in a subject or clinical investigation subject administered a pharmaceutical product and which does not necessarily have a causal relationship with this treatment. An AE can therefore be any unfavorable and unintended sign (including an abnormal laboratory value), symptom, or disease (new or exacerbated) temporally associated with the use of a medicinal (investigational) product, whether or not related to the medicinal (investigational) product.

Thus, any new sign, symptom or disease, or any clinically significant worsening of an existing sign, symptom or disease compared to the condition at the first visit (including disease treated), should be considered as an AE. Lack of efficacy is not considered as an AE.

Each new episode of a chronic disease (e.g., hay fever, allergy, etc.) should be reported as a new AE.

#### Notes:

- Any new sign or symptom reported by the subject that appears after accidental or intentional overdose or misuse should also be reported as an AE.
- Whenever possible, a diagnosis should be reported on the AE form rather than the signs, symptoms or abnormal laboratory values associated with the AE. However, a diagnosis should be reported only if, in the Investigator's judgment, it is relatively certain. Otherwise, symptoms, signs, or laboratory values should be used to describe the AE.
- Pregnancy is not to be considered as an AE; however, it is an important medical event that must be monitored as described in Section 6.3.6.2.5.

Events NOT Meeting the AE Definition

Medical or surgical procedure (e.g., endoscopy, appendectomy): the condition that leads to the procedure is the AE.

GALDERMA R&D RD.06.SPR.204245 V00 18AUG2021 Page 62 of 104

### 6.3.6.1.2 Serious Adverse Events

If an event is not an AE per definition above, then it cannot be an SAE even if serious conditions are met. A serious adverse event (SAE) is any untoward medical occurrence that:

- Results in death,
- Is life-threatening,
- Requires inpatient hospitalization or prolongation of existing hospitalization,
- Results in persistent or significant disability/incapacity, or
- Is a congenital anomaly/birth defect.

Important medical events that may not result in death, be life-threatening, or require hospitalization may be considered an SAE when, based upon appropriate medical judgment, they may jeopardize the safety of the subject and may require medical or surgical intervention to prevent one of the outcomes listed in this definition. Examples of such events are intensive treatment in an emergency room or at home for allergic bronchospasm, blood dyscrasia, or convulsions that do not result in hospitalization.

Note: The term "life-threatening" refers to an event in which the subject was at risk of death at the time of the event; it does not refer to an event that hypothetically might have caused death if it were more severe.

Inpatient hospitalization is considered to have occurred if the subject has had to stay for a night at the hospital. The criterion for prolongation of hospitalization is also defined as an extra night at the hospital. Hospitalization may not constitute sufficient grounds to be considered as an SAE if it is solely for the purpose of diagnostic tests (even if related to an AE), elective hospitalization for an intervention that was already planned before subject enrollment in the clinical trial, admission to a day-care facility, social admission (e.g., if the subject has no place to sleep), or administrative admission (e.g., for a yearly examination).

# 6.3.6.1.3 Adverse Events of Special Interest

An AESI is a noteworthy treatment-emergent event for the particular study drug that can be appropriate for the Sponsor to monitor closely. It could be serious or non-serious and AESIs could include events that might be potential precursors or prodromal symptoms for more serious medical conditions in susceptible individuals.

The AEs of Special Interest for this protocol are pre-defined as follows:

- Erythema, scaling, dryness, stinging/burning, and other related cutaneous AEs which lead to permanent treatment discontinuation
- Suspicion of allergic contact reaction related to the study drug (see Section 6.3.6.2.4)

GALDERMA R&D RD.06.SPR.204245 V00 18AUG2021 Page 63 of 104

For AESIs, the Investigator is required to complete the AESI Form, within 72 hours of the event, and follow the AESI reporting procedures in Section 6.3.6.1.3 even if the event is considered non-serious according to the usual regulatory criteria.

For suspected sensitizations associated with topical study medication use, follow the rechallenge with assigned topical study drug patch test procedures in Section 6.3.6.2.4 (and subsequent ingredient patch testing, if the rechallenge with assigned topical study drug is positive or equivocal).

### 6.3.6.1.4 Unexpected Adverse Drug Reaction

According to ICH E6, an unexpected adverse drug reaction is defined as an adverse reaction, the nature or severity of which is not consistent with the applicable study drug information (e.g., reference safety information in Investigator Brochure, package insert/summary of product characteristics, etc).

Expectedness of SAEs related to trifarotene will be assessed against the trifarotene package insert.

## 6.3.6.1.5 Adverse Event Reporting Period

The clinical trial period during which AEs must be reported is the period from when the subject signed the ICF to the end of the subject's participation.

The Sponsor should be informed if the Investigator becomes aware of any unusual safety information or any safety information that appears to be drug-related involving a subject who has participated in a clinical trial, even after a subject has completed the clinical trial. The Investigator should be diligent in looking for possible latent safety effects that may not appear until a medication has been discontinued.

### 6.3.6.1.6 Adverse Event Severity

Severity is a clinical determination of the intensity of an AE and not of a disease.

The Investigator is to classify the intensity of AEs using the following definitions as a guideline for all AEs. For this classification, the Investigator will take into account the possible range of the intensity of the event and report the grade of intensity which is the most appropriate according his medical judgment.

Mild Awareness of signs or symptom, but easily tolerated.

Moderate Discomfort, enough to cause interference with usual activity

Severe Incapacitating with inability to work or perform usual activity

GALDERMA R&D RD.06.SPR.204245 V00 18AUG2021 Page 64 of 104

## 6.3.6.1.7 Relationship to the Study Drugs and/or Clinical Trial Procedures

The investigator is to determine whether there is a reasonable causal relationship between the occurrence of the AE and exposure to the study drug and/or clinical trial procedures (eg. use of moisturizer). Medical judgment should be used to determine the relationship, considering all relevant factors including the pattern of reaction, temporal relationships, positive challenge or rechallenge, relevant medical history, and confounding factors such as co-medication or concurrent diseases.

The expression "reasonable causal relationship" is meant to convey in general that there are facts or arguments to suggest a causal relationship (ICH E2A, Section IIIA 1).

The relationship assessment for an AE is to be completed using the following definitions as a guideline for all AEs occurring during clinical trials conducted or sponsored by GALDERMA R&D:

### Reasonable possibility:

- According to the Investigator, there is a reasonable possibility (i.e., suggestive evidence or arguments) that there is a causal relationship irrespective of the dose administered between:
  - The study drug (investigational product or vehicle) and the AE,
  - The clinical trial protocol procedure and the AE.

## No reasonable possibility:

• No suggestive evidence or arguments can be identified regarding a causal relationship between the study drugs.

For AEs graded to be a reasonable possibility of being related to study drugs, the Investigator will determine whether they are related to topical or oral study drug, or both.

## 6.3.6.2 Reporting Procedures

### 6.3.6.2.1 Procedures for Reporting Adverse Events

The collection of AEs is from the time that a subject sign the ICF to their final visit.

At each post enrollment visit, the Investigator (or sub-Investigator) will question the subject about AEs using an open non-persuasive question to elicit reporting of AEs, for example: "Have you noticed any change in your health since the last visit?" Directed questioning and examination will then be performed, as appropriate.

Any AE occurring during the AE reporting period, whether it is related to the study drug or not, will be recorded immediately in the source document, and described on the Adverse Event Form

GALDERMA R&D RD.06.SPR.204245 V00 18AUG2021 Page 65 of 104

along with the date of onset, severity, relationship to the study drug, and outcome, without omitting any requested and known information. Additional information may be requested under certain circumstances. Adverse Events assessed as related to the treatment will be monitored until they are completely or satisfactorily resolved. Other AEs will be monitored until the last visit if they are not resolved or satisfactorily resolved.

The Investigator will obtain and maintain in the subject's files all pertinent medical records, information and medical judgment from colleagues who assisted in the treatment and follow-up of the subject. If necessary, the Investigator will contact the subject's personal physician or hospital staff to obtain further details.

For SAEs (see Section 6.3.6.2.2), AESIs (see Section 6.3.6.2.3), and pregnancies (see Section 6.3.6.2.5), refer to the sections listed for further reporting requirements.

## 6.3.6.2.2 Procedure for Reporting a Serious Adverse Event

For an SAE occurring during the period of the clinical trial, regardless of whether it is related to the treatment or not, and of whether it is expected or not, the Investigator must do the following:

- 1. Take prompt and appropriate medical action, if necessary. The safety of the subject is the first priority.
- 2. Immediately inform Parexel Pharmacovigilance of the event (within 24 hours of knowledge of the event) by fax or email and discuss further actions to be taken. Email is the preferred method.

Parexel Pharmacovigilance:

email: NorthAmerica [contact] (preferred method)

or

Safety [contact]

- 3. Complete the Adverse Event Form provided in the CRF as fully as possible.
- 4. Ensure that the event is classified as an SAE in the CRF.
- 5. Print and complete the Serious Adverse Event Form available in the electronic data capture (EDC) system as PDF document. Fax or scan and send by e mail the completed form, accompanied by any other relevant information or medical records (e.g., laboratory test results) within 24 hours to Parexel Pharmacovigilance. The demographics, medical history, previous and concomitant therapies, and adverse event pages of the CRF must be completed and available for review in the EDC system at the time of the report.
- 6. Monitor and record the progress of the event until it resolves or reaches a clinically stable outcome, with or without sequelae. For follow-up evaluations, notify Parexel

GALDERMA R&D RD.06.SPR.204245 V00 18AUG2021 Page 66 of 104

Pharmacovigilance of updates within 24 hours. Serious Adverse Events will be monitored until the Investigator and Sponsor agree that the event is satisfactorily resolved.

- 7. Obtain and maintain in his/her files all pertinent medical records, information, and medical judgments from colleagues who assisted in the treatment and follow-up of the subject. If necessary, contact the subject's personal physician or hospital staff to obtain further details.
- 8. Inform Parexel Pharmacovigilance of the final outcome of the event. Send a revised or updated Serious Adverse Event Form and Adverse Event Form, if appropriate.
- 9. Comply with the applicable regulatory requirement(s) related to the reporting of SAEs to the Institutional Review Board (IRB) / Independent Ethics Committee (IEC).

# 6.3.6.2.3 Procedure for Reporting an Adverse Event of Special Interest

For any treatment-emergent AESI occurring during the period of the clinical trial, whether related to the treatment or not, and whether expected or not, the Investigator is to do the following:

- 1. Take prompt and appropriate medical action, if necessary. The safety of subjects is the first priority.
- 2. Immediately inform Parexel Pharmacovigilance of the event by fax or email and discuss further actions to be taken (Section 6.3.6.2.2).
- 3. Complete the Adverse Event Form provided in the CRF as fully as possible.
- 4. Ensure that the event is classified as an AESI in the CRF and that all relevant CRF pages have been updated (e.g. medical history, concomitant medications, procedures, AE, etc.)
- 5. Print the Adverse Event form. Fax or scan and send by e mail the completed form, accompanied by any other relevant information or medical records (e.g. laboratory test results) within 72 hours to Parexel Pharmacovigilance. The demographics, medical history, previous and concomitant therapies, and adverse event pages of the CRF must be completed and available for review in the EDC system at the time of the report.
- 6. Monitor and record the progress of the event until it resolves or reaches a clinically stable outcome, with or without sequelae. For follow-up evaluations, notify Parexel Pharmacovigilance. AESIs will be monitored until the Investigator and Sponsor agree that the event is satisfactorily resolved.
- 7. Obtain and maintain in his/her files all pertinent medical records, information, and medical judgments from colleagues who assisted in the treatment and follow-up of the subject. If necessary, contact the subject's personal physician or hospital staff to obtain further details.
- 8. Inform Parexel Pharmacovigilance of the final outcome of the event. Send a revised or updated Adverse Event Form, if appropriate.

6.3.6.2.4 Procedures for Suspected Allergic Contact Reaction to Topical Study Medication (Rechallenge Patch Test and Ingredient Patch Testing)

If a subject experience a suspected allergic contact reaction associated with topical study medication use, the following actions should be taken to characterize the event:

- Stop study medication.
- Take a picture of the affected area and the non-affected surrounding skin with the supplied photo equipment and upload to the vendor's portal.
- Document the event as an Adverse Event of Special Interest, report the event within 72 hrs to Parexel Pharmacovigilance (see Section 6.3.6.2.3).
- The subject continues to be followed for scheduled study visits while awaiting the rechallenge test results.

## a) Rechallenge with Assigned Topical Study Medication

- 1. After all signs and symptoms of AESI have resolved and after a minimum of two weeks from last topical dose application, perform a rechallenge test with the assigned topical study drug. Scheduling on a Monday or Tuesday is ideal, as it ensures the 48-hour and 72-96 hour follow-up assessments occur on weekdays (Table 10).
- 2. Ensure the subject has not been under any treatment with corticosteroids or antihistamines of any route of administration the Week before testing.
- 3. Ensure that the skin on the back has not been exposed to the sun or artificial ultraviolet sources the Week before testing.
- 4. Apply an appropriate quantity of the assigned topical study drug to fill in the cupule of the test chamber to a naïve zone on the back either the right or left side of the center line (or the inner forearm if the back cannot be tested). If no test chamber is available on site, patch test units will be provided by the Sponsor or designee. Apply an empty test chamber as a control for the rechallenge test with assigned topical study drug (note: an empty test chamber will not be needed for ingredient testing, if such test is warranted, as the Sponsor/designee will provide one or more controls for testing). The use of semi-occlusive conditions depends on the irritant potential of the study product and the intensity of the reaction that was observed. The method to be used should be discussed with the Medical Monitor.

Choose a skin site that was not previously involved in the inflammatory skin reaction. Cover the test chamber for 48 hours with a hypoallergenic tape.

- 5. Subject should be informed about avoiding exercise, showers, application of toiletries products, etc., to keep the test system dry
- 6. After 48 hours, remove the test chamber and evaluate the site and take photos after each reading (Table 10):

- at approximately 30 minutes after patch test removal (1st reading) and,
- 24 to 48 hours later (i.e., 72 or 96 hours after application) (2nd reading).
- If the result of the second reading is equivocal, the Investigator or at the Sponsors request, may perform an optional 3rd reading at 96 to 120 hours later (i.e., 6 to 7 days after application of the patch).
- Pictures of each reading and the reading results should be sent to Parexel Pharmacovigilance and medical monitor.

**Table 10:** Patch Testing Readout Schedule

Day Patch Test Starts	1st reading + Photographs	2nd reading + Photographs	3rd reading (optional) + Photographs
	48 hours after study product application (30 minutes after patch test removal)	72 to 96 hours after study product application (24 to 48 hours after patch test removal)	6 or 7 days after study product application (96 to 120 hours after patch removal)
If test starts on Monday :	Wednesday	Thursday or Friday	Monday
If test starts on Tuesday :	Thursday	Friday	Monday or Tuesday

Refer to Table 11 for the scoring system at each readout used by the International Contact Dermatitis Research Group (ICDRG) (Spiewak, 2008).

**Table 11:** Grading System for Suspected Allergic Contact Reaction

Score	Morphology	Interpretation
-	No skin changes in the tested area	Negative
?	Faint, non-palpable erythema	Doubtful reaction
+	Palpable erythema (moderate edema or infiltrate), papules not present or scarce, vesicles not present	Weak positive reaction
++	Strong infiltrate, numerous papules, vesicles present	Strong positive reaction
+++	Erythema, infiltration, confluent vesicles, bullae or ulceration	Extreme positive reaction
ir	Inflammation sharply limited to the exposed area, lack of infiltrate, small petechiae, pustules, and efflorescences other than papules and vesicles	Irritant reaction
Nt		Not tested

7. At the last reading, the investigator will refer to Table 12 and provide an overall interpretation regarding a possible sensitization reaction, which is based on results using the ICDRG scale.

### **Table 12:** Investigator Overall Conclusion of Suspected Sensitization

	Sensitization Reaction						
0	Negative (absence of reaction or might be irritant reaction)						
1	Equivocal						
2	Positive						

- 8. In case of absence of negative reaction, the subject may resume study treatment if appropriate. Otherwise, the subject should complete end of study procedures.
- 9. If the rechallenge with assigned topical study medication is positive or equivocal, notify Parexel Pharmacovigilance and medical monitor immediately. Except in specific situations, ingredient patch testing of the topical study medication will be initiated as directed by the Sponsor (with individual ingredients at different concentrations if applicable, and possibly negative and positive controls) after a minimum of an additional two weeks (but not later than 6 months) and after all signs and symptoms have resolved.
  - The Sponsor will provide a letter to the investigator with blinded results for ingredient testing, and further instructions how the subject and his/her primary care provider can determine test results, while maintaining blinding of the investigator and site staff (Appendix 14.6).

Note: Ingredient testing will follow the above process beginning with step number 4, with testing of the individual ingredients (and controls, as applicable). The Sponsor or designee will provide the necessary supplies for ingredient testing. Given the delay when ingredient testing supplies may arrive, subjects may receive treatment for their acne other than the study drug, and should stop all acne therapy a minimum of 1 Week before ingredient testing.

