## ADVERSE REACTIONS

#### 6.1 Clinical trials experience

Because clinical trials are conducted under widely varying conditions, adverse reaction rates observed in the clinical trials of a drug cannot be directly compared with rates in the clinical trials of another drug and may not reflect rates observed in practice. In the three Phase 3 clinical trials, a total of 1673 subjects with acne vulgaris on the face and trunk, 9 years and older were exposed to AKLIEF Cream. Of these, 1220 subjects were treated once daily for up to 12 weeks and 453 were treated once daily for up to 1 year.

Adverse reactions reported in the 2 randomized, double-blind, vehicle-controlled 12-week clinical trials in ≥1.0% of subjects treated with AKLIEF Cream (and for which the rate exceeded the rate for vehicle), as well as the corresponding rates reported in subjects treated with the vehicle cream are presented in Table 1.

Table 1. Adverse Reactions Occurring in ≥ 1.0% of Subjects with Acne Vulgaris of the Face and Trunk in the Two 12-week Phase 3 Clinical Trials

Preferred Term	AKLIEF Cream (N=1220)	Vehicle Cream (N=1200)
Application site irritation	91 (7.5)	4 (0.3)
Application site pruritus	29 (2.4)	10 (0.8)
Sunburn	32 (2.6)	6 (0.5)

Additional adverse reactions that were reported in more than one subject treated with AKLIEF Cream (and at a frequency <1%) included application site pain, application site dryness, application site discoloration, application site rash, application site swelling, application site erosion, acne, dermatitis allergic, and erythema.

In the one-year, open-label safety trial that included 453 subjects 9 years and older, with acne vulgaris of the face and trunk, the pattern of adverse reactions for AKLIEF Cream was similar to that experienced in the 12-week controlled trials. A total of 12.6% of subjects had at least one adverse reaction during the trial, and 2.9% of subjects had an adverse reaction leading to treatment discontinuation. The most common adverse reactions (≥ 1% of subjects) for the entire trial were application site pruritus (4.6%), application site irritation (4.2%), and sunburn (5.5%). The frequency of adverse reactions decreased over time.

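### Step 8 of the patch-test procedure reads backwards: on the protocol's own scale, an equivocal or positive rechallenge permits restarting study drug and a negative one ends participation

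*Protocol*

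**What the plan says.** Protocol section 6.3.6.2.4 covers suspected allergic contact reactions. The first action listed is "Stop study medication". Once signs have resolved, and at least two weeks after the last application, part a) has the assigned product patch-tested on the subject.

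- **Table 11** grades each reading. The lowest grade, "No skin changes in the tested area", is interpreted as Negative.
- **Step 7** has the investigator give an overall conclusion from Table 12 at the last reading.
- **Table 12** has three categories: 0 is "Negative (absence of reaction or might be irritant reaction"), 1 is Equivocal and 2 is Positive.
- **Step 8**, directly below that table, decides what happens to the subject: "In case of absence of negative reaction, the subject may resume study treatment if appropriate. Otherwise, the subject should complete end of study procedures".
- **Step 9** begins "If the rechallenge with assigned topical study medication is positive or equivocal" and requires immediate notification of pharmacovigilance and the medical monitor, followed in most cases by ingredient patch testing.
- **The Note to step 9** says that, while testing supplies are awaited, "subjects may receive treatment for their acne other than the study drug".

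The SAP lists suspected allergic contact reaction as an adverse event of special interest (section 4.11.2) but says nothing about restarting treatment.

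**The concern.** Within this procedure Negative is a defined result meaning that no sensitization was found. Step 8 makes restarting conditional on that result being absent. An investigator who applies the scale as printed would have grounds to re-expose a subject whose rechallenge was equivocal or positive, and would take a cleared subject off the study.

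The sentence matters because it is the only explicit rule on restarting after a rechallenge. No other section of the protocol or SAP expressly forbids restarting after a positive result, so nothing elsewhere overrides it. The trial plans about 20 sites in three countries and enrols minors from age 13, so a safety instruction should not depend on each site noticing a slip.

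**Working it through.** The plan states no figure on this point. The check is one of logic, followed by a rough count of how often the instruction might be used.

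**1. Run each Table 12 score through step 8 as worded.** The condition for restarting is that the result is not negative.

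| Table 12 score | Is a negative result absent? | Step 8 as worded | Direction implied by step 9 and its Note |
|---|---|---|---|
| 0 Negative | No | End of study procedures | May restart if appropriate |
| 1 Equivocal | Yes | May restart if appropriate | Do not restart; escalate |
| 2 Positive | Yes | May restart if appropriate | Do not restart; escalate |

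All three rows are reversed.

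**2. Check the intended direction against the rest of the protocol.**

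- Drug is stopped on suspicion alone (6.3.6.2.4, opening actions).
- Section 6.3.6.1.3 and step 9 both treat positive or equivocal as the result that needs further testing.
- The Note to step 9 has such subjects on acne treatment other than study drug.
- Exclusion criterion 11 (section 5.3.3) bars anyone with known or suspected allergy to the product.

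These all point the same way, so the error lies in step 8 and not in the tables.

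**3. Expected number of cases (illustration only).** The documents give no rate for suspected allergic contact reactions. The nearest figure is in the label, Appendix 14.9, section 6.1. Allergic dermatitis is in the list introduced by "Additional adverse reactions that were reported in more than one subject treated with AKLIEF Cream (and at a frequency <1" per cent), and 1220 subjects were treated for up to 12 weeks in the two vehicle-controlled trials. More than one subject means at least 2. Below 1% of 1220 means at most 12, since 13/1220 = 1.07%.

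With about 60 trifarotene subjects (protocol section 7.2), expected cases = 60 × p and the chance of at least one = 1 − (1 − p)^60:

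- Low end: p = 2/1220 = 0.0016. Expected 0.10 cases; chance of at least one 0.094.
- High end: p = 12/1220 = 0.0098. Expected 0.59 cases; chance of at least one 0.447.

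The high end is the arithmetic ceiling of the label's wording, not an observed count. Suspected reactions may be more frequent than coded allergic dermatitis. Treatment here lasts 24 weeks, and vehicle subjects can also react, so the true number could differ.

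**The case against.** The best defence is that the phrase in step 8 was never meant as the Table 12 result. Neither table uses those exact words together. The sentence may run two parts of the score 0 entry into one, or may use the word negative in its everyday sense of untoward. On either reading the instruction is correct. Step 9 comes immediately after it, and a dermatologist would probably notice that ending the study for non-reactors and restarting reactors makes no sense.

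There are also real safeguards:

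- Restarting is only allowed where appropriate.
- Step 6 of the rechallenge procedure says "Pictures of each reading and the reading results should be sent to Parexel Pharmacovigilance and medical monitor".
- The special-interest event procedure (6.3.6.2.3) requires immediate contact with pharmacovigilance to discuss further action, and monitoring until investigator and sponsor agree that the event is resolved.
- Either the investigator or the sponsor may withdraw a subject (5.3.4).

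It can also be said that the 9% to 45% range is the chance of at least one allergic dermatitis case. Harm would further require an equivocal or positive rechallenge and literal compliance with step 8, and the documents give no rate for either.

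Much of this stands. The benign reading is probably what the author intended, the safeguards make an actual wrong restart unlikely, and the range must not be read as a probability of harm. It does not rescue the wording: the benign reading requires setting aside a term defined in the table printed just above. Step 9 also does nothing for the cleared subject, because it applies only to positive or equivocal results.

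**Conclusion.** The concern holds. It is a drafting error in an operative safety instruction: taken on the protocol's own scale, step 8 gives the wrong direction for every possible result. The conclusion rests on reading negative as Tables 11 and 12 define it and on the absence of any other restart rule in the two documents.

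Its practical size is small. Fewer than one case among trifarotene subjects would be expected under the illustrative rates, and several people would have to accept the perverse reading before anyone was harmed. There is no consequence for alpha, power or sample size. It should still be corrected, because a literal reading allows re-exposure of a possibly sensitized subject.

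**What to change.** Replace step 8 with wording tied to the Table 12 score, for example:

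> If the overall conclusion is negative (Table 12 score 0), the subject may resume study treatment if appropriate. If it is equivocal or positive (score 1 or 2), study drug must not be resumed; follow step 9 and complete end of study procedures.

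The explicit bar on restarting spells out what the existing alternative branch of step 8 would already require once its condition is corrected. A lighter version corrects only the condition, to a negative conclusion (score 0), and leaves the rest of the sentence to cover scores 1 and 2. The fuller version is safer because nothing else in the protocol states the bar.

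The cost is one or two sentences in a protocol amendment or a clarification letter to sites. Sample size, visits and analysis are unchanged.
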